4.4.2 Data Collection and Follow-up for Withdrawn Subjects

Data will be collected from the researchers involved in this protocol and stored in an encrypted computer. Follow-up for withdrawn subjects will be subjected to the time point they withdrew.

5 Study Device

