5.5 Prior and Concomitant Therapy

Although BBB opening is reversible and transient, it may lead to unintended diffusion of pharmaceutical molecules into the brain parenchyma. To avoid such potential effects, non-critical medications will be withheld prior to treatment and until closure of the BBB is confirmed (at least 24 hours before and after the procedure). For critical medications, medication withholding will be judged based on the subject's diagnosis, condition, and medication type.

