In the second visit, BBB opening will be attempted in a designated facility in the hospital using the described FUS system. First, a baseline cavitation signal will be obtained prior to microbubble injection. Then, an intravenous injection of Definity microbubbles under the FDA guidelines will be administered as a bolus or via a syringe pump and the cavitation signal will be monitored and recorded during sonication at acoustic parameters well below the FDA safety limit (MI = 0.4). In this EFS, we will target the prefrontal cortex (PFC). PFC has been shown to be affected by AD pathology, leading to deficits in attention, spatial memory and planned movements. Although we do not aim to treat AD in this EFS, PFC was selected as the targeted structure due to its relevance to this condition, its size and ease of targeting with our singleelement transducer. A follow-up MRI (with and without contrast) will be acquired the same day after BBB opening to ensure treatment safety and efficacy. Finally, two blood samples will be collected before and after treatment through an intravenous catheter or a finger prick. Blood analysis will be performed to test whether there are acute changes in the blood test results due to the FUS application. Based on our animal studies, there is an acute increase in reticulocytes, platelets and eosinophils after FUS treatment, possibly due to the BBB restoration process. Blood samples will be used to test whether these changes in blood chemistry occur also in humans. Blood samples will be stored and analyzed to detect potential changes in Alzheimer's Disease biomarkers and other compounds that may exit the brain parenchyma because of the blood-brain barrier opening (e.g. exosomes). All time points will be compared to baseline acquired during screening.

6.3 Visit 3

A follow-up MRI (with and without contrast) will be performed three days (± 1 day) after treatment to confirm BBB closure and to assess safety. A blood sample will be collected through an intravenous catheter or a finger prick, to test for short-term changes in blood chemistry and cell count.

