6.4 Visit 4/5

Follow-up visits will be required three weeks (± 1 week) and three months (± 2 weeks) after treatment to assess long-term safety, amyloid plaque load and cognitive function through behavioral tests. Two follow-up PET/CT scan using Amyvid (¹⁸F-Florbetapir) will be performed; one 3 weeks (± 1 week) post-FUS and one 3 months (± 2 weeks) post-FUS, to test for potential reduction in the amyloid plaque load. A blood sample will be also collected through an intravenous catheter or a finger prick, to test for long-term changes in blood chemistry and cell count. One follow-up visit following a single FUS treatment was deemed sufficient by the attending neurologist.

7 Statistical Plan

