8.1 Definitions

Unanticipated adverse device effect (UADE): Any serious adverse effect on health or safety or any lifethreatening problem or death caused by, or associated with, a device, if that effect, problem, or death was not previously identified in nature, severity, or degree of incidence in the investigational plan or IDE application (including a supplementary plan or application), or any other unanticipated serious problem associated with a device that relates to the rights, safety, or welfare of subjects.

Associated with the investigational device: There is a reasonable possibility that the adverse effect may have been caused by the investigational device.

Life-threatening adverse effect: Any adverse effect that places the subject, in the view of either the investigator or the sponsor, at immediate risk of death from the effect **as it occurred**. It does not include a reaction that, had it occurred in a more severe form, might have caused death.

Serious adverse effect: An adverse effect is considered "serious" if, in the view of either the investigator or the sponsor, it results in any of the following outcomes:

- death
- a life-threatening AE
- inpatient hospitalization or prolongation of existing hospitalization
- a persistent or significant disability/incapacity
- a congenital anomaly/birth defect.

Unanticipated adverse effect: Any adverse effect, the nature, specificity, severity, or frequency of which is not consistent with the risk information in the clinical study protocol or elsewhere in the current IDE application.

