8.2 Recording of Adverse Device Effects

All observed or volunteered adverse effects (serious or non-serious) and abnormal test findings, regardless of treatment group, if applicable, or suspected causal relationship to the investigational device or, if

applicable, other study treatment or diagnostic product(s) will be recorded in the subjects' case histories. For all adverse effects, sufficient information will be pursued and/or obtained so as to permit 1) an adequate determination of the outcome of the effect (i.e., whether the effect should be classified as a serious adverse effect) and; 2) an assessment of the causal relationship between the adverse effect and the investigational device or, if applicable, the other study treatment or diagnostic product(s).

Adverse effects or abnormal test findings felt to be associated with the investigational device or, if applicable, other study treatment or diagnostic product(s) will be followed until the effect (or its sequelae) or the abnormal test finding resolves or stabilizes at a level acceptable to the sponsor-investigator.

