8.5 Stopping Rules

Redundant safety features have been added to the hardware of the device, as grounding for the transducer, safety switch for the amplifier and function generator. Additionally, we will incorporate safety valves in our software. For any signs showing safety risk including high cavitation dose in the acoustic monitoring or unstable vital signs, the device can be stopped from the computer user interface and/or an emergency stop button. Treatment will be stopped in the case of any reaction of the subject to the ultrasound exposure or microbubble infusion. Pulse oximetry will be used during MRI scans to mitigate the risk of anaphylactic reaction to MRI contrast agents. Potential adverse effects have been grouped according to their severity in the following table:

Severity	Adverse effect			
Severe	Local hemorrhage	Edema	Intracranial infection	Status epilepticus
Moderate	Emesis	Dizziness	Allergic reaction	Nausea
Mild	Skull heating	Injection site bruising	Headache	

The investigation will be paused and the relevant authorities will be notified in case of any death, life threatening event, or any other serious adverse event described in the table above (including disability or clinically significant manifestation of local hemorrhage or edema) due to the procedure. An episode of status epilepticus during treatment will terminate the session immediately.

If the selected ultrasound settings (i.e., MI of 0.4) do not successfully open the BBB in 3 subjects, FDA will be contacted via a submission of an IDE supplement, to discuss revising the protocol's focused ultrasound parameters or increase the number of subjects.

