8.6 Medical Monitoring

Medical monitoring will be performed by the neurologist of this study, [name], MD at the Taub Institute of Alzheimer's Disease and Aging at Columbia. [name] or any other trained radiologist will be present during the trial and will assess the subject's clinical status during therapy. In the case of an allergic or any other reaction (e.g. status epilepticus) to the therapy, the study will be immediately discontinued. Resuscitation equipment will be readily available in the study room, in case of a serious adverse event.

Subjects will be monitored with follow-up MRI scans to confirm BBB opening and closing and PET scans to estimate amyloid plaque load. Should the MRI or PET brain scans of this study have incidental findings (e.g. brain tumor, subarachnoid hemorrhage, or structural abnormality) the subject will be immediately withdrawn from the study and directed for clinical care. MRI scans will be examined by [name], who is a certified in Diagnostic Radiology and is the Section Chief of Neuroradiology. MRI scan examination by [name] will occur as soon as possible but no later than two weeks following receipt of the image.

If there are any incidental findings deemed by the clinical-investigator to be "life-threatening" or "important but not severe", both the subject and the subject's personal primary care physician will be notified. Communication may be initially verbal, followed by a formal written communication. The significance of the incidental finding will be determined by the clinical-investigator and communicated to the subject accordingly. Incidental findings of clinical significance and the management of such findings should be documented in the research records of this study.

At the time of a continuing review, if incidental findings were noted during the previous approval period, the principal investigator of this study will provide the IRB with the following information: the number of required review images, a list of the subject study numbers, the type of scan, the date of the scan, a description of the incidental finding of clinical significance, the date of communication with the subject and the outcome, if known.

If the participants expressed severe depression or suicidal ideation in the course of their visit, the subject will be urgently assessed by the study clinician and appropriate referrals will be made. In addition, we will exclude the participant from the study.

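### Section 8.6 makes subarachnoid hemorrhage on any study scan an incidental finding requiring withdrawal, and no rule says whether 8.6 or the adverse-effect sections govern a bleed new since Visit 1

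*Combined protocol and SAP*

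**What the plan says.** Section 8.6 refers to follow-up MRI and PET scans and then sets a rule for incidental findings on the study's MRI or PET brain scans: "e.g. brain tumor, subarachnoid hemorrhage, or structural abnormality) the subject will be immediately withdrawn from the study and directed for clinical care". Section 8.6.1 repeats the rule for MRI, but its examples leave out subarachnoid hemorrhage.

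Other sections deal with the same kind of finding as a possible harm:

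- Section 1.5.1 names hemorrhage and edema as possible unintended effects of ultrasound at high intensity, and section 3.4 makes MRI one of the two safety tools.
- Section 8.1 counts an effect as associated with the device when "There is a reasonable possibility that the adverse effect may have been caused by the investigational device".
- Section 8.2 records every abnormal test finding whatever its suspected cause, and asks for a causal assessment of every adverse effect. Findings felt to be associated with the device or another study product "will be followed until the effect (or its sequelae) or the abnormal test finding resolves or stabilizes at a level acceptable to the sponsor-investigator".
- Section 8.5 puts local hemorrhage and edema in the severe row of its table. It pauses the investigation for serious events "including disability or clinically significant manifestation of local hemorrhage or edema) due to the procedure".

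On withdrawal, section 4.4.2 says: "Follow-up for withdrawn subjects will be subjected to the time point they withdrew". The visits at stake are the day-3 MRI (section 6.3), done "after treatment to confirm BBB closure and to assess safety", and the 3-week and 3-month visits (section 6.4), held "after treatment to assess long-term safety, amyloid plaque load and cognitive function through behavioral tests".

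**The concern.** A subarachnoid bleed first seen after sonication fits two descriptions in the plan. Under 8.6 it is a named example of an incidental finding, and the subject leaves the study at once. Under 8.2 and 8.5 it is an abnormal finding or adverse effect, to be assessed for cause and, if associated, followed until it resolves or stabilizes. No sentence ranks the two, and none uses the Visit 1 scan to separate a new bleed from one already there.

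This is a six-subject safety and feasibility study, and section 8.6.1 acknowledges that long-term effects in the human brain have not been studied. A subject with a new bleed is the one whose later safety data matter most. Followed literally, the withdrawal rule could remove that subject from the remaining safety assessments and possibly from the analysis.

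**Working it through.** No event rate or power figure enters this point. The check is a comparison of the sections and a count of visits.

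**1. When does the 8.6 rule apply?** Section 4.1 uses the initial MRI to settle enrollment, and section 4.2 excludes acute or chronic hemorrhage, apparently tolerating up to four lobar microbleeds. A subarachnoid hemorrhage at Visit 1 should therefore already exclude the subject. The withdrawal rule matters mainly on later scans, where such a bleed is likely to be new.

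**2. What does each route require?**

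| | Incidental finding (8.6) | Adverse effect (8.2, 8.5) |
|---|---|---|
| Judgement asked for | Clinical significance | Seriousness and cause |
| Subject | Withdrawn, referred to care | Associated findings followed until resolved or stable |
| Study | No consequence stated | Paused if serious or clinically significant and due to the procedure |

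The routes can both apply. They conflict on one matter: whether the subject stays under study follow-up.

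**3. Do 8.2 and 8.5 settle it?** Only in part. Follow-up under 8.2 depends on a finding being felt to be associated, and no test based on the Visit 1 scan is given. Section 8.5 speaks of local hemorrhage, of clinical significance and of an event due to the procedure. A subarachnoid or symptom-free bleed is not clearly covered.

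**4. How many assessments could be missed?** Three are scheduled after the same-day MRI:

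- day-3 MRI: 3 ± 1, so day 2 to 4;
- 3-week visit: 21 ± 7, so day 14 to 28;
- 3-month visit: ± 2 weeks.

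Section 8.6 allows up to two weeks from receipt to examine an MRI. Assume that images are received on the day of the scan and that withdrawal ends study visits:

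- Bleed on the same-day MRI, read before the day-3 scan: 3 of 3 missed.
- Same MRI read at the limit (day 14): the day-3 MRI has already been done, so at most 2 of 3.
- Bleed on the day-3 MRI, read at once: 2 of 3.
- Day-3 MRI read at the limit (2 + 14 = day 16, to 4 + 14 = day 18): 1 or 2 of 3, because the 3-week visit may already have taken place.

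Three is thus the upper bound and needs a prompt read.

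**5. Analysis population.** Section 7.3 defines one population, for subjects who complied with all required processing. The 75% criterion in section 7.1 refers to cases and names no population. A subject withdrawn before the later visits could be judged not to have complied.

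**The case against.** The strongest reply is that the plan already handles a new bleed. Section 8.2 captures every abnormal test finding whatever its cause, 8.5 lists local hemorrhage as severe, and section 6.2 schedules the same-day MRI to check safety. A bleed found there is what the scan was looking for, so few investigators would call it incidental. The list in 8.6 is only illustrative, and 8.6.1 omits subarachnoid hemorrhage. Most of this stands. A reader might infer that nothing in the plan treats hemorrhage as an adverse effect; the documents do not support that. What remains is that 8.6 names this bleed, orders withdrawal, and has no precedence rule.

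Second, section 4.4.2 is ambiguous. It can mean that follow-up depends on when the subject withdrew, not that it stops, and 8.2 makes no exception for withdrawn subjects. This also stands, so the missed visits are a possibility and not a stated consequence.

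Third, a reader might infer that the incidental label delays an urgent IRB report, since 8.6 lists such findings at continuing review. Section 8.3.2 reserves its 2-day and 5-day IRB reports for unanticipated events and problems. Hemorrhage is a listed potential effect, so fast IRB reporting may not apply on either route. The separate 10-business-day report to NIMH covers serious adverse events.

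Fourth, section 7.3 does not say that it governs safety, and it asks for randomization in a trial that section 5.3 describes as single-arm and non-random. The loss from analysis is therefore a risk of the wording and not a rule.

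**Conclusion.** The point holds as an overlap with one real conflict. Section 8.6, read as written, withdraws a subject whom 8.2 would follow, and nothing says which prevails for a hemorrhage new since Visit 1. The possible loss is up to three scheduled safety assessments for an affected subject, and possibly that subject's place in the only defined population.

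The upper bound assumes that the bleed is classed as incidental, that the same-day MRI is read before the day-3 scan, and that 4.4.2 is taken to end study visits. The documents do not establish that any of these would happen, and a careful investigator would probably classify a new bleed correctly. It would go too far to say that the plan discards hemorrhages or has no adverse-effect route for them. This is a cheap improvement to the plan, worth making because the study's purpose is safety and the number of subjects is six.

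**What to change.** 1. In 8.6 and 8.6.1, limit incidental findings to those present on the Visit 1 scan, or judged to have no reasonable possibility of a link to the procedure.
2. State there that hemorrhage or edema new since Visit 1 is handled as an adverse effect under 8.2 and 8.5. The existing pause threshold in 8.5 can stay as it is.
3. State that such a subject remains in the safety follow-up already scheduled, with a cross-reference in 4.4.2. The research PET can be optional, and the subject may decline further visits.
4. In 7.3, state that all treated subjects count in the safety results and in the 75% criterion for safe opening.

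The cost is a few sentences, with no scans or visits beyond those planned. There are two downsides. A subject with a new bleed is asked to keep attending, and the study may occasionally pause for an event later judged unrelated, which would delay the remaining subjects.

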4.1 Inclusion Criteria

AD patients will be recruited in person and have to be over 50 years of age and able to give consent. Patients diagnosed with early stages of AD or with MCI will be included in our study. Other more severe symptomatic patients will be eligible to enroll, as long as they have the ability to consent for their participation. Screening is essential and will be performed by our collaborator and neurologist of the study, [name], MD at the Taub Institute of Alzheimer's Disease and Aging at Columbia. After the initial screening we will acquire MRI scans as part of the study and finalize enrollment or exclusion of the patient. Inclusion criteria thus include:

- Age greater than 50 years old.
- Diagnosis of early AD or MCI at minimum. All following criteria must be met:
 - Probable MCI or AD consistent with criteria outlined in (McKhann *et al* 2011, Petersen *et al* 2018).
 - MMSE score between 12 and 26.
 - Modified Hachinski Ischemia Scale (MHIS) score of <= 4
 - Short form Geriatric Depression Scale (GDS) score of ≤ 6 .
 - PET scan confirming amyloid plaque load using Amyvid (¹⁸F-Florbetapir).
- Ability to provide informed consent.

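### The 8.6 exclusion for severe depression or suicidal ideation also reaches sonicated subjects, and the plan does not protect their remaining safety assessments

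*Combined protocol and SAP*

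**What the plan says.** Section 8.6 (Medical Monitoring) sets the trigger: "If the participants expressed severe depression or suicidal ideation in the course of their visit". Two consequences follow. The first is clinical: "the subject will be urgently assessed by the study clinician and appropriate referrals will be made". The second concerns participation: "In addition, we will exclude the participant from the study". Nothing limits the second to screening, and the rule stands in the monitoring section, not among the exclusion criteria in 4.2.

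Four other sections bear on what happens next.

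- **4.4.2:** "Follow-up for withdrawn subjects will be subjected to the time point they withdrew". It does not say which assessments continue.
- **8.2:** All adverse effects are recorded, whatever the suspected cause. A follow-up duty is added for a subset: "Adverse effects or abnormal test findings felt to be associated with the investigational device", or with other study treatment or diagnostic products, "will be followed until the effect (or its sequelae) or the abnormal test finding resolves or stabilizes".
- **7.3:** The only analysis population is a protocol-compliant one. No all-treated safety set is defined.
- **6.2 to 6.4:** There is one FUS treatment, at Visit 2, aimed at the prefrontal cortex. An MRI follows the same day and another at day 3. Visits at 3 weeks and 3 months cover long-term safety, amyloid PET and cognitive tests.

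**The concern.** Before sonication, excluding such a subject works as an eligibility rule and costs no safety information on the device. After sonication the same sentence removes a treated subject because of something that may be an effect of treatment. With only one treatment there is no later sonication to prevent, so what exclusion takes away is assessment.

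The assessments at risk matter to this study. Section 3.4 bases primary safety on MRI and neurocognitive tests, and 8.6.1 acknowledges that long-term effects in the human brain have not been studied. Whether a subject's data go missing would depend on having had a possible adverse effect, so the loss is informative. The subjects who remain would look healthier than the treated group was, and with six patients one case is enough to change the picture.

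**Working it through.** **The plan's own figure.** Section 7.1 gives six subjects for a paired t-test (difference 200 mm³, SD 50 mm³, α = 0.05, power 0.95). Taking 50 as the SD of the difference and a two-sided test, exact power is 0.908 at n = 3 and 0.998 at n = 4. Four subjects would suffice, and six meets the stated target. That calculation concerns opening volume. The present point needs only the denominator of six.

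**What is forfeited, by time of the event.** I take Visit 4 as the 3-week visit and Visit 5 as the 3-month visit, giving 6 × 2 = 12 planned long-term subject-visits. Suppose one subject is excluded and nothing further is collected on schedule.

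| Event voiced at | Scheduled assessments still due | Long-term subject-visits lost |
|---|---|---|
| Visit 2, after sonication | rest of that day's tests, day-3 MRI and blood, 3-week and 3-month visits | 2/12 = 16.7% |
| Visit 3 | rest of Visit 3, 3-week and 3-month visits | 2/12 = 16.7% |
| Visit 4 | rest of Visit 4, 3-month visit | 1/12 = 8.3%, plus anything unfinished at Visit 4 |
| Visit 5 | rest of Visit 5 | none beyond anything unfinished at Visit 5 |

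So 16.7% is a ceiling for one case.

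**Effect on what is reported.** Suppose one of six sonicated subjects has the event and is then excluded.

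- All sonicated subjects counted: 1/6 = 16.7%, exact two-sided 95% interval 0.4% to 64.1%.
- Excluded subject dropped: 0/5 = 0%, with upper limit 1 − 0.025^(1/5) = 52.2% on the same two-sided basis.

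The second line arises only if the summary is confined to completers or to the 7.3 population, and only if an excluded subject is held not to have complied with all required processing.

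**Effect on other late outcomes.** For an outcome with no events seen, the one-sided 95% upper bound is 1 − 0.05^(1/n).

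- n = 6: 1 − 0.05^(1/6) = 39.3%
- n = 5: 1 − 0.05^(1/5) = 45.1%

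**The sections side by side.** Section 8.6 takes the subject out. Section 4.4.2 leaves open what continues, and 4.4.1 describes only withdrawal by the patient, so it is unclear whether an exclusion by the investigators falls under 4.4.2 at all. Section 8.2 keeps following the event if it is judged associated, with no exception for excluded subjects. That judgement is made in an unblinded single-arm study (5.3, 5.7), and the table of potential adverse effects in 8.5 lists no mood event. Section 8.2 follows the effect itself and does not preserve the scheduled MRI or cognitive tests. Section 7.3 then offers no analysis set that would certainly include the subject.

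**The case against.** The strongest reply is 8.2. A reader might infer from 8.6 that exclusion ends a subject's safety follow-up, or that all data on the event's course are lost. The documents do not support either reading. Every adverse effect must be recorded, and one judged associated with the device must be followed until it resolves or stabilizes. An adverse-effect listing should therefore still show the event. This part of the reply stands.

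A reader might also take 4.4.2 as stopping follow-up at withdrawal. Its wording is ambiguous: it may mean only that follow-up depends on when the subject left.

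Two further cautions stand. An entry requirement of "Short form Geriatric Depression Scale (GDS) score of" 6 or less makes later severe depression likely to be a change since screening, but does not show that suicidal ideation is new. Section 6.2 links the prefrontal target to attention, spatial memory and planned movement, not to mood, so a treatment effect is a possibility only. The endpoint in 3.4 does not name mood either; the link to it runs through the cognitive tests that would be missed.

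Finally, the gap is wider than this one sentence. Sections 8.6 and 8.6.1 also withdraw subjects for incidental imaging findings, again without saying what follow-up continues. That is a reason to word the repair for all sonicated subjects; it does not remove the point.

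What the reply leaves untouched is the loss of assessments still due on schedule, the follow-up of events judged unrelated, and the missing all-treated safety set.

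**Conclusion.** The point holds in a limited form. Followed as written, 8.6 removes already sonicated subjects because of a possible treatment-emergent effect, prevents no further sonication, and puts their remaining scheduled safety assessments at risk. Sections 4.4.2 and 7.3 do not protect those data, and 8.2 does so only in part.

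For one case, the loss is at most 16.7% of long-term subject-visits, about 8.3% if the event arises at Visit 4, and essentially nothing at the end of Visit 5. The 0/5 against 1/6 contrast is conditional on how safety is tabulated, which the plan does not state. The documents give no expected frequency of such events, so these figures show the consequence of one case and not its likelihood. The assumptions are that both long-term visits take place and that exclusion is applied as ending scheduled visits.

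**What to change.** Reconcile 4.4.2, 7.3, 8.2 and 8.6 by separating exclusion from further study treatment from the end of safety data collection.

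- In 8.6 and 4.4.2, state that for any subject already sonicated, the safety assessments already scheduled continue to be collected where the subject consents and the clinician considers it appropriate.
- In 7.3, add a safety population of all sonicated subjects, use it for every safety table, and show missing visits and the reason for each.

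The urgent assessment and referral in 8.6 stay as written. No clinical management rule is proposed: how the exclusion applies after treatment is for the investigators to settle when they reconcile these sections.

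The cost is a few sentences and no added visits. The small downside is that an unwell subject may need flexible timing or may still miss visits.
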